9.3.3. Missing and Partial AE Start and Stop Dates

Imputation rules for missing or partial AE start and end dates are outlined in Section 6.8.3.

9.3.4. Summaries of Adverse Events

Adverse event verbatim text will be coded and classified by system organ class (SOC) and preferred term (PT) using the MedDRA (Version 20.0). AE summary tables will use the following algorithms for counting subject events within the summary tables:

- Any event row: Each subject with an event is counted only once at the maximum grade although they may have several events. For drug related AE tables, each subject with an event is counted only once at the most related although they may have several events.
- System organ class rows: Each subject is counted only once at the maximum grade at each system organ class level although they may have several different preferred term events within the same SOC.
- Preferred term rows: Each subject is counted once within each unique preferred term at the maximum grade. Subjects experiencing the same AE preferred term several times with different grades would only be counted once with the maximum grade.

For partially missing start or stop dates, the imputation rule specified in Section 6.8.3 will be applied before assessing if an AE was a TEAE.

TEAE data will be summarized by treatment and overall.

9.3.4.1. Overview and Summaries of Adverse TEAEs

An overall summary table (overview) of all TEAEs will be presented, summarizing:

- Total Number of TEAEs
- Total Number of TESAEs
- Total Number of TEAESIs
- Number of Subjects with at Least One TEAE
- Number of Subjects with at Least One Related TEAE
- Number of Subjects with at Least One Severe (Grade 3) TEAE
- Number Subjects with at Least One TEAE Leading to Treatment Discontinuation
- Number Subjects with at Least One TEAE Leading to Death
- Number of Subjects with at Least One TESAE
- Number of Subjects with at Least One Related TESAE
- Number of Subjects with at Least One TEAESI

[name], Ltd Statistical Analysis Plan, Version 2.0

TEAEs will be summarized by SOC and PT. For SOC, each subject is counted only once at each SOC level although they may have several different PT events within the same SOC. Likewise for any PT event, each subject with an event is counted only once although they may have several PT events that are the same.

Summaries for the common TEAEs will be created for TEAEs with an incidence [> 1%] in at least one treatment group. Common TEAEs will be summarized by SOC and PT.

Summaries for TEAEs by maximum severity will be created for all TEAEs. Severity will be summarized by SOC and PT. If a subject has multiple occurrences of the same SOC or PT, then only the most severe event will be summarized in the tables for that SOC or PT. TEAEs with missing severity treatment will be counted as severe.

Summaries for TEAEs by the closest relationship to study drug will be created for all TEAEs. Relationship to study drug will be summarized by SOC and PT. TEAEs will be classified as "Related" to study drug if relationship is categorized as Definitely Related, Probably Related or Possibly Related. Otherwise TEAEs will be classified as "Not Related". If a subject has multiple occurrences of the same SOC or PT, then only the most related event will be summarized in the tables for that SOC or PT. TEAEs with missing relationship to study drug will be counted as "Related".

TEAE outcomes will be summarized by SOC and PT. TEAE outcome categories are:

- Recovered/Resolved
- Recovered/Resolved with Sequelae
- Not Recovered/Not Resolved
- Fatal
- Unknown

If a subject has multiple occurrences of the same SOC or PT, then only the most negative outcome will be summarized in the tables for that SOC or PT. TEAEs with missing outcome will be counted as unknown. Most negative outcome in terms of decreasing rank are: Fatal, Not Recovered/Not Resolved, Recovered/Resolved with Sequelae, Recovered/Resolved, Unknown.

TEAE actions taken with study drug will be summarized by SOC and PT. TEAE action taken with study drug categories are:

- Dose Not Changed
- Drug Withdrawn
- Dose Interrupted
- Dose Reduced
- Dose Increased
- Unknown

If a subject has multiple occurrences of the same SOC or PT, then only the most negative action taken with study drug will be summarized in the tables for that SOC or PT. TEAEs with missing action taken with study drug will be counted as unknown. Most negative action taken with study drug in terms of decreasing rank are: Drug Withdrawn, Dose Interrupted, Dose Reduced, Dose Increased, Dose Not Changed, and Unknown.

TEAE actions taken with subject will be summarized by SOC and PT. TEAE action taken with subject categories are:

[name], Ltd Statistical Analysis Plan, Version 2.0

- None
- Hospitalization
- Change in Concomitant Medication
- Other
- Unknown

If a subject has multiple occurrences of the same SOC or PT, then only the most negative action taken with subject will be summarized in the tables for that SOC or PT. TEAEs with missing action taken with subject will be counted as unknown. Most negative action taken with study drug in terms of decreasing rank are: Hospitalization, Change in Concomitant Medication, Other, None, Unknown.

Severe TEAEs collected during the course of the study will be summarized by SOC and PT.

Treatment Emergent Serious Adverse Events (TESAEs) collected during the course of the study will be summarized by SOC and PT.

TEAEs leading to study discontinuation will be summarized by SOC and PT.

Treatment Emergent Adverse Events of Special Interest (TEAESIs) will be summarized by SOC and PT.

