### 11.5.3 Adverse Events

All AEs occurring during the study will be recorded and classified on the basis of Medical Dictionary for Regulatory Activities (MedDRA) terminology. Treatment-emergent adverse events (TEAEs) are AEs with an onset on or after the date of the first study product administration. For the safety population, all reported TEAEs will be summarized by treatment group, the number and percent of subjects reporting events, system organ class (SOC), preferred term (PT), severity, relationship to study product, and seriousness. When summarizing TEAEs by causality and severity, each subject will be counted only once within a system organ class or a preferred term by using the event with the greatest relationship and highest severity within each classification

Additionally, treatment-related TEAEs will be summarized for each treatment group by SOC and PT, and further by severity. A TEAE will be considered treatment-related if it is reported as possibly, probably, or definitely related to study treatment.

SAEs will be listed by subject. In addition, a list of subjects who prematurely discontinued from the study due to an AE will be provided.

All information pertaining to AEs noted during the study will be listed by subject, detailing verbatim term given by the investigator, preferred term, system organ class, onset date, resolution date, maximum severity, seriousness, action taken regarding study product, corrective treatment, outcome, and drug relatedness. The event onset will also be shown relative (in number of days) to date of first administration.

AEs related to study procedures done before study product administration will be provided in a data listing.

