11. APPENDIX

11.1. Table of Contents for Data Display Specifications

Refer to the MS Excel spreadsheet.

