Table 14.2.2.1	Subject Compliance - Total Number of Applications, Number and Percentage of Subjects who are Compliant for the Baseline to Week 12 evaluation period	Safety	N/A	Unique
Table 14.2.2.2.1	Local Cutaneous Safety Evaluation by Treatment Group and Visit-Non-lesional erythema	Safety	N/A	Unique
Table 14.2.2.2.2	Local Cutaneous Safety Evaluation by Treatment Group and Visit-Peeling	Safety	N/A	Repeat
Table 14.2.2.2.3	Local Cutaneous Safety Evaluation by Treatment Group and Visit-Dryness	Safety	N/A	Repeat
Table 14.2.2.2.4	Local Cutaneous Safety Evaluation by Treatment Group and Visit-Burning	Safety	N/A	Repeat
Table 14.2.2.2.5	Local Cutaneous Safety Evaluation by Treatment Group and Visit-Stinging	Safety	N/A	Repeat
Table 14.2.2.2.6	Local Cutaneous Safety Evaluation by Treatment Group and Visit-Itching	Safety	N/A	Repeat
Table 14.2.2.3.1	Local Cutaneous Safety Evaluation by Treatment Group and Visit- Excluding Subjects with Signs or Symptoms at Baseline-Non-lesional erythema	Safety	N/A	Repeat
Table 14.2.2.3.2	Local Cutaneous Safety Evaluation by Treatment Group and Visit- Excluding Subjects with Signs or Symptoms at Baseline-Peeling	Safety	N/A	Repeat
Table 14.2.2.3.3	Local Cutaneous Safety Evaluation by Treatment Group and Visit- Excluding Subjects with Signs or Symptoms at Baseline -Dryness	Safety	N/A	Repeat
Table 14.2.2.3.4	Local Cutaneous Safety Evaluation by Treatment Group and Visit- Excluding Subjects with Signs or Symptoms at Baseline -Burning	Safety	N/A	Repeat
Table 14.2.2.3.5	Local Cutaneous Safety Evaluation by Treatment Group and Visit- Excluding Subjects with Signs or Symptoms at Baseline -Stinging	Safety	N/A	Repeat
Table 14.2.2.3.6	Local Cutaneous Safety Evaluation by Treatment Group and Visit- Excluding Subjects with Signs or Symptoms at Baseline -Itching	Safety	N/A	Repeat

Display Number	Title	Populations	Subgroup	Unique/ Repeat
Safety Tables				
Table 14.3.1.1	Overall Summary of Treatment Emergent Adverse Events	Safety	N/A	Unique
Table 14.3.1.2	Summary of Treatment Emergent Adverse Events by System Organ Class and Preferred Term	Safety	N/A	Unique
Table 14.3.1.2.1	Summary of Treatment Emergent Adverse Events by System Organ Class, Preferred Term and Severity	Safety	N/A	Repeat
Table 14.3.1.2.2	Summary of Treatment Emergent Adverse Events by System Organ Class, Preferred Term and Relationship to Study Drug	Safety	N/A	Repeat

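### The SAP omits, without saying so, the by-severity breakdown of treatment-related TEAEs that Protocol 11.5.3 specifies, so its planned tables do not in general give severe related counts by arm

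*SAP*

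**What the plan says.** Protocol 11.5.3 first plans summaries of all TEAEs by SOC, PT, severity, relationship and seriousness. It then adds a separate requirement: "treatment-related TEAEs will be summarized for each treatment group by SOC and PT, and further by severity". Events judged possibly, probably or definitely related count as treatment-related.

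SAP 9.3.4.1 handles the two dimensions one at a time:

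- Severity: "Summaries for TEAEs by maximum severity will be created for all TEAEs".
- Relationship: "Summaries for TEAEs by the closest relationship to study drug will be created for all TEAEs". This is reduced to Related or Not Related, by SOC and PT.
- Severe events: "Severe TEAEs collected during the course of the study will be summarized by SOC and PT", whatever their cause.
- Overview: one row for subjects with a related TEAE and another for subjects with a severe TEAE. The only joint row involving relationship is for related serious events, and seriousness is not severity.

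The display index in SAP 11.2 follows the same pattern. Table 14.3.1.2.1 is "Summary of Treatment Emergent Adverse Events by System Organ Class, Preferred Term and Severity" and Table 14.3.1.2.2 is "Summary of Treatment Emergent Adverse Events by System Organ Class, Preferred Term and Relationship to Study Drug". SAP 2 undertakes to report deviations from the approved SAP. The SAP has no section listing its own changes from the protocol.

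**The concern.** TEAEs are one of the two primary safety endpoints in SAP 3.2.1, and the study's purpose is to compare the tolerability of DFD-03 Lotion with that of Tazorac Cream. How severe the product-related events are in each arm is a natural question for the report, and the protocol specified a table that answers it.

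If the SAP is run exactly as written, that table is not produced. Because the SAP's promise covers only departures from the SAP itself, nothing would prompt the study report to mention the omission. A reader of the summary tables would see how many subjects had a related event and how many had a severe one, but not in general how many had an event that was both.

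**Working it through.** The plan gives no figure to reproduce here. There are two questions: does any SAP text supply the split, and if not, how much do the planned tables still reveal?

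**1. Could the counting rules in SAP 9.3.4 supply the split?** That section says: "System organ class rows: Each subject is counted only once at the maximum grade at each system organ class level". It has a matching rule for PT rows. For the any-event row of drug-related tables it counts each subject at the most related event. SAP 9.3.4.1 likewise keeps only the most related event per SOC or PT in the relationship summary. These rules say which event represents a subject. They do not create a severity breakdown among related events.

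**2. What do the separate tables determine?** For one table row in one arm, let:

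- T = subjects with the event
- R = subjects with a related event
- S = subjects with a severe event
- k = subjects with both related and unrelated events in that row
- X = subjects with a severe related event

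The tables give T, R and S, but not k. Then

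max(0, R + S − T − min(k, S)) ≤ X ≤ min(R, S).

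Enumerating all configurations for T = 5, 8 and 15 with k = 0 to 3 reproduced these limits. The enumeration took one event per subject, plus k subjects with one related and one unrelated event.

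**3. Inputs.** The planned active arms have 50 subjects each and the vehicle arms 25 each (Protocol 6.4, SAP 4.4). Protocol 8 reports the commonest reactions to tazarotene cream 0.1% in 10% to 30% of subjects, which is 0.10 × 50 = 5 to 0.30 × 50 = 15 subjects in an active arm. The documents give no severe-event rate, so S, R and k below are assumptions, and T = 15 is the top of that range.

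**4. Results for one PT row, T = 15 and S = 3**

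| R | k | Lower limit | Upper limit | X |
|---|---|---|---|---|
| 15 | 0 | 15 + 3 − 15 = 3 | 3 | exactly 3 |
| 15 | 1 | 15 + 3 − 15 − 1 = 2 | 3 | 2 to 3 |
| 14 | 0 | 14 + 3 − 15 = 2 | 3 | 2 to 3 |
| 13 | 0 | 13 + 3 − 15 = 1 | 3 | 1 to 3 |
| 12 | 0 | 12 + 3 − 15 = 0 | 3 | 0 to 3 |

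If S = 0, then X = 0 and nothing is lost. The same limits apply to moderate-or-severe events. With T = 15, R = 12, 6 such subjects and k = 0, the count lies between 12 + 6 − 15 = 3 and 6.

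**5. Direct demonstration.** Take 10 subjects with one PT, 4 severe and 6 related. In one dataset the 4 severe subjects are all among the 6 related; in the other they are the 4 unrelated. The total events, the subjects with any, a related or a severe TEAE, the PT-by-severity counts and the PT-by-relationship counts are identical. X is 4 in the first and 0 in the second. The planned summaries therefore do not in general fix X.

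**The case against.** The strongest reply is that little is lost in practice, and most of it stands. Listings 16.2.7.1 and 16.2.7.2 show severity beside relationship for every event, so about 150 subjects can be tallied by hand. Tables 14.3.1.3 and 14.3.1.4 do the same for serious events and discontinuations. The 0 to 3 tolerance scores grade local irritation directly, by arm and visit. The study is descriptive and not powered, so no test or decision rule uses the missing count. The commonest reactions are known effects of tazarotene, so R close to T is plausible. Protocol 8.2 lets intermittent events be recorded once, which tends to keep k small. In such rows the count is exact or nearly so.

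This limits the consequence but does not remove the mismatch. The protocol specified a summary by arm, and a subject listing is not one. The tolerance scores are only a partial substitute: they describe signs and symptoms at visits, while AE severity grades interference with activity (Protocol 8.3.1) and also draws on diaries and spontaneous reports.

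Three stronger readings are tempting and not supported:

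- A reader might infer that the any-event and SOC rows leave the severe related count anywhere from 0 to S. That treats each row alone. Severity and relationship are also tabulated by PT, and a lower limit from a PT row carries upward. If one PT row fixes the count at 3, the SOC and any-event counts are at least 3.
- A reader might infer that related TEAEs are not summarized, or that data are withheld. Table 14.3.1.2.2 summarizes them by SOC and PT, and the listings show the rest.
- A reader might treat the display index as proof of the omission. It also leaves out summaries that the SAP text promises, such as outcomes, actions taken and overall tolerance. For its table of contents SAP 11.1 says "Refer to the MS Excel spreadsheet", and that file is not among the documents. The finding rests on the text of SAP 9.3.4 and 9.3.4.1; the index merely agrees.

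**Conclusion.** The mismatch is real and minor. Protocol 11.5.3 specifies treatment-related TEAEs by severity. SAP 9.3.4.1 plans severity and relationship only as separate summaries over all TEAEs, and does not record the change. The planned tables therefore do not in general give the by-arm number of subjects with a severe, or moderate-or-severe, related TEAE.

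How wide the gap would be in the actual data cannot be stated, because it depends on event counts that the documents do not give. It closes in any row where all events are related or none is severe. The information remains available in the listings, so the cost of leaving the plan alone is a hand tally and an unreported departure from the protocol. The documents do not show whether the omission was intended.

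**What to change.** Add one table to SAP 9.3.4.1 and to the display index: treatment-related TEAEs (possibly, probably or definitely related) by arm, SOC, PT and maximum severity, with the maximum taken over related events only. Use the SAP's existing rules, which count a missing severity as severe and a missing relationship as related. If the sponsor prefers not to add the table, record the omission as a departure from Protocol 11.5.3.

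Two additions are optional: a footnote giving the number of subjects affected by the missing-value rules, since SAP 6.5.2 says missing safety data are not imputed, and an overview row for subjects with at least one severe related TEAE.

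The cost is one extra table. Severity and relationship are already recorded for each event on the AE eCRF (Protocol 8.2), so no new data are needed.

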3.2. Study Endpoints

3.2.1. Primary Endpoints

The primary safety endpoints are:

- Local Cutaneous Safety Evaluation Data (dryness, non-lesional erythema, peeling, stinging, burning, and itching). Reactions on the face were assessed separately from those on the chest/back/shoulders.
- Treatment-Emergent Adverse Events (TEAEs).

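### Ranking an unknown or missing AE outcome or action as least negative lets the SAP's per-subject summaries show a favourable result that is not established

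*SAP*

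**What the plan says.** SAP 9.3.4.1 (Overview and Summaries of Adverse TEAEs) promises summaries of outcome, action taken with study drug and action taken with subject, by SOC and PT. For outcome, "If a subject has multiple occurrences of the same SOC or PT, then only the most negative outcome will be summarized in the tables". Missing values go to the Unknown category: "TEAEs with missing outcome will be counted as unknown", and the section says the same for both action variables.

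Each variable has its own ranking, from most to least negative:

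- Outcome: "Most negative outcome in terms of decreasing rank are: Fatal, Not Recovered/Not Resolved, Recovered/Resolved with Sequelae, Recovered/Resolved, Unknown".
- Action with study drug: "Drug Withdrawn, Dose Interrupted, Dose Reduced, Dose Increased, Dose Not Changed, and Unknown".
- Action with subject: "Hospitalization, Change in Concomitant Medication, Other, None, Unknown".

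Unknown is last in all three. Two other missing-value rules in the same section go the other way. For severity, "TEAEs with missing severity treatment will be counted as severe". For causality, "TEAEs with missing relationship to study drug will be counted as" Related.

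**The concern.** When only the most negative category is displayed, the position of Unknown decides whether undetermined information survives the collapse to one value per subject. In last place, Unknown loses to every known category, including the favourable one. The table then reports a subject as recovered, as having no dose change, or as needing no action, when one of the events behind that row has no established result.

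Safety is the purpose of this trial. SAP 3.2.1 ("The primary safety endpoints are") names the local cutaneous evaluation and TEAEs. A reader of the outcome table would reasonably take a subject counted as resolved to mean that all of that subject's events in the row are known to have resolved. Under this rule that is not so.

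**Working it through.** The documents give no figure on this point, so there is none to reproduce. The check has three parts.

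**1. Every pair of outcomes.** Five outcome categories give 5 × 4 / 2 = 10 unordered pairs. The six pairs without Unknown do not depend on where Unknown is ranked. The four pairs with Unknown are:

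| Two events in one row | Shown under the SAP | Shown if Unknown ranks just above Recovered/Resolved |
|---|---|---|
| Fatal + Unknown | Fatal | Fatal |
| Not Recovered + Unknown | Not Recovered | Not Recovered |
| Recovered with Sequelae + Unknown | Recovered with Sequelae | Recovered with Sequelae |
| Recovered + Unknown | **Recovered** | **Unknown** |

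One pair in ten changes. By the same reasoning, action with study drug has six categories and 6 × 5 / 2 = 15 pairs, of which only Dose Not Changed + Unknown changes. Action with subject has five categories and 10 pairs, of which only None + Unknown changes. A single event is displayed as recorded under either order, and a subject whose events are all Unknown is shown as Unknown.

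**2. Comparison within the SAP.**

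| Item | Handling of missing or unknown |
|---|---|
| Severity (9.3.4.1) | Missing takes the worst level |
| Relationship (9.3.4.1) | Missing counts as Related |
| AE stop date (6.8.3) | Unknown outcome is grouped with ongoing; no stop date is imputed |
| Outcome and both actions (9.3.4.1) | Missing becomes Unknown, the least negative rank |

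Only the last row treats lack of information as better than a known good result.

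**3. Illustrative size.** Assume that a subject has *k* independent events in one row, each Unknown or missing with probability *u* and otherwise resolved. Neither *u* nor independence comes from the documents.

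- P(any Unknown) = 1 − (1 − u)^k
- P(shown as Unknown under the SAP) = u^k, because all events must be Unknown
- P(shown as resolved despite an Unknown) = 1 − (1 − u)^k − u^k

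For k = 2 the last line equals 2u(1 − u); for k = 3 it equals 3u(1 − u). For k = 1 it is 0.

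| u | k = 2: any Unknown | k = 2: shown as resolved despite an Unknown | Share of those with any Unknown | k = 3: shown as resolved despite an Unknown |
|---|---|---|---|---|
| 2% | 3.96% | 3.9% | 99% | 5.9% |
| 5% | 9.75% | 9.5% | 97% | 14.3% |
| 10% | 19.0% | 18.0% | 95% | 27.0% |
| 20% | 36.0% | 32.0% | 89% | 48.0% |

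For every 50 subjects with two events in one row, 50 × 0.0392 = 2.0 (u = 2%) to 50 × 0.32 = 16 (u = 20%) would be affected. Fifty is the planned size of each active arm. The number with two events in one row is not known and is presumably smaller, and the count falls in proportion.

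**The case against.** The best defence is that the variables differ in kind. Severity has three levels and relationship four, with no Unknown level, so a missing value must be placed in a substantive category. Outcome and both actions do have an Unknown category, and SAP 6.5.2 says that missing safety data are not imputed. Ranking Unknown last can then be read as showing the most negative *known* result. This explains why missing is mapped to Unknown. It does not explain why Unknown should rank below the favourable category, since the table does not say that it is restricted to known results.

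The protocol also limits how often the rule matters. Section 8.2 allows intermittent AEs to be recorded once, which reduces repeat records within a PT. Section 8 requires SAEs, product-related AEs and AEs leading to product discontinuation to be followed until the outcome is determined or attempts are exhausted. Both points stand as limits on size. Neither removes the case: SAP 9.3.4 itself anticipates several PTs in one SOC, and six local signs and symptoms can each generate an AE if worse than at Baseline (Protocol 7.6). Which of these share a SOC is not shown in the documents.

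A reader might infer three stronger conclusions that the documents do not support:

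- *Unresolved events are hidden.* Not Recovered/Not Resolved ranks second, so a recorded unresolved event is never displaced by a resolved or unknown one. Only undetermined outcomes are lost, and some of those may in fact have resolved.
- *The rule favours DFD-03.* It applies identically in all four arms. A between-arm bias would need different rates of unknown outcomes or of multiple events, and nothing in the documents indicates that.
- *The primary safety results are compromised.* TEAE counts, severity, relationship and local tolerability scores do not use these rankings, and the AE listings carry each event's outcome, including a code for Unknown.

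**Conclusion.** The point holds as a minor specification defect in secondary descriptive tables. The three rankings err in the favourable direction and make outcome and action summaries look somewhat better in absolute terms in every arm. The effect is confined to subjects with two or more events in the same SOC or PT, at least one Unknown or missing, and the rest in the most favourable category. The collapse rule and the inconsistency follow directly from the SAP text. The percentages depend wholly on the assumed *u* and on independence, and serve only to show that where the conditions are met, nearly all such subjects lose the Unknown label (89% to 99% with two events).

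**What to change.** Change three ranking lines in SAP 9.3.4.1 so that Unknown, including missing, sits above only the most favourable category:

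- Outcome: below Recovered/Resolved with Sequelae and directly above Recovered/Resolved.
- Action with study drug: below the known dose changes and directly above Dose Not Changed.
- Action with subject: below Other and directly above None.

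Unknown should go no higher. Placing it directly after Not Recovered/Not Resolved would change two outcome pairs instead of one, and the second would replace a confirmed sequela with Unknown.

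While editing, add the outcome and action tables to the display index in SAP 11.2, which lists none although 9.3.4.1 promises them.

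The cost is three lines of text plus those table entries, with no new data. SAP section 2 allows revision until the plan is finalised before database lock; after that, the change would be noted in the study report. The one downside is that slightly more subjects will appear as Unknown.
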